Evaluation of the impact of the HLNatural, Inc. Immune Support Product in Reducing the Length of Cold Symptoms in Adults Suffering from the Common Cold

NCT04103099

Day Month Year July, 17th 2019

Evaluation of the impact of the HLNatural, Inc. Immune Support Product in Reducing the Length of Cold Symptoms in Adults Suffering from the Common Cold

Sponsored by: HLNatural, Inc.

Principal Investigator:[name]

Version Number
Version 1.1

Day Month Year July, 17th 2019

Statement of Compliance

The study will be carried out in accordance with Good Clinical Practice (GCP) as required by the following:

- U.S. Code of Federal Regulations applicable to clinical studies (45 CFR 46)
- ICH GCP E6
- Completion of Human Subjects Protection Training
- NIH Clinical Terms of Award

Refer to:

http://www.hhs.gov/ohrp/humansubjects/quidance/45cfr46.htm#46.

http://www.fda.gov/cder/quidance/959fnl.pdf

http://grants.nih.gov/grants/guide/notice-files/NOT-OD-01-061.html

http://cme.cancer.gov/c01/

SIGNATURE PAGE

The signature below constitutes the approval of this protocol and the attachments and provides the necessary assurances that this trial will be conducted according to all stipulations of the protocol, including all statements regarding confidentiality, and according to local legal and regulatory requirements and applicable US federal regulations and ICH guidelines.

Principal I	nvestigator:		
Signed:		Date:	
	Name		
Project M	anager:		
Signed:		Date:	
	Name		
Sponsor:			
Signed:		Date:	
	Name		
Statisticia	n		
Signed:		Date:	
	Name		

Title: Evaluation of the impact of the HLNatural, Inc. Immunity product in reducing

the length of cold symptoms in adults suffering from the common cold

Population: The study will consist of at least 200 participants who self-identify as satisfying

the inclusion criteria. The geography of participant enrollment will be spread

across the United States.

Number of Sites: This is a single (virtual) site study.

Study Type Single site, prospective, one arm observational study of Minimal Risk.

Study Duration: The duration of the study is expected to be 6 months depending on the speed of

enrollment.

Participant Duration: The duration of participation for each participant is expected to be 90 days from

the day of study start date.

Objectives: The purpose of this study is to demonstrate whether or not this test product will

reduce the duration of cold symptoms. This trial will gather data on performance of the test product. These data will be used to describe the performance currently, and potentially to design a two-arm trial in the future.

Primary Endpoints:

 The primary endpoint will be time to freedom from cold symptoms, with the clock starting at the onset of the cold. The primary analysis will be a Kaplan-Meier analysis of time to absence of all symptoms, based on the participants' self-report. There is no control group for the primary analysis.

Secondary Endpoints:

- Secondary endpoints involve the duration and severity of the separate cold symptoms.
- Net Promoter Score.
- Adverse events will be summarized.
- An additional data presentation will consist of results from both Treatment and Control in similar studies appearing in the literature. There will be no formal statistical comparison of results from this study and historical studies.

Table OF Contents

2.1. Background Information

The primary hypothesis of the present study is that daily supplementation with the Immune Support test product will reduce the time to freedom from cold symptoms.

The common cold is a viral infection most commonly caused by the Rhinovirus; however, it can be caused by a number of other virus families as well. Cold viruses are transmitted via airborne and fomite routes and has a seasonal distribution in the autumn and winter; although it can occur at any time of the year. It is the most common infectious disease in the US and industrialized countries. Symptoms resulting from the common cold include nasal stuffing, sneezing, sore throat and coughing. These symptoms are a result of the cytokines, especially interleukin-8 (IL-8), released In response to infection with rhinovirus. IL-8 has been shown to cause up-regulation of adhesion molecule receptors on neutrophils and can cause neutrophil degranulation in addition to chemotaxis of eosinophils, T-lymphocytes, and basophils. Thus, cytokine elaboration, especially IL-8, plays an important role in the influx of polymorphonuclear cells (PMN) into nasal secretions and development of these symptoms of the common cold. Studies of volunteers inoculated with rhinovirus also demonstrated that symptoms during infection correlated with an increase in the concentration of IL-8 in nasal secretions. [38]

While implications on physical health are significant, the economic consequences of the common cold are also vast; direct costs associated with the cold amount to \$17 billion in the United States through more than 500 million viruses. Additionally, its microeconomic impact on workplace productivity is also prevalent. The United States population misses up to 26 million days of work due to the common cold, a cause of lost productivity. [10, 26, 31]

Every year, tens of millions of dollars are spent trying to help prevent the common cold. While the common cold has associated medications that can help ease the symptoms, there has been no

therapy to treat the viral infections comprehensively. Particular drug classes, such alpha agonists (phenylephrine) and nonsteroidal anti-inflammatory drugs (NSAIDs), have helped improve symptoms in conjunction with common cold onset. However, several side effects are known for these as well as other over-the-counter products. NSAIDs have been shown to have effects on many organ systems in the body. The side-effects include dyspepsia, peptic ulcer disease, bleeding, modest worsening of hypertension, edema, myocardial infarction, and many others. [39] While oral alpha-agonists (phenylephrine) have shown to cause anxiety, dizziness, headache, insomnia, nervousness, restlessness.[40] Additionally, antibiotics are not recommended as colds are viral, not bacterial. [10, 31]

HLNatural, Inc. was formed to create an herbal product that is designed to avoid side effects as well as unnecessary synthetics, sweeteners, and preservatives found in over the counter remedies today. As such, HILMA created a line of products containing high-quality, well-researched ingredients creating a unique product unlike anything else on the market. This Immune Support Product is formulated with ingredients with demonstrated potential to reduce duration and symptoms associated with the common cold. The products combine ingredients previously reported as potentially beneficial into an easy to consume powder drink-mix designed for intake twice a day. The ingredients in the test product are 1) Echinacea 2) Ivy Extract, 3) Camu Camu, 4) Ginger, 5) Turmeric, 6) Zinc, 7) Monk Fruit Extract, 8) Natural Flavor, 9) Guar Gum, 10) Citric Acid. Listed below are the 6 active ingredients of the test product. All ingredients are Generally Recognized as Safe (GRAS) by the FDA.

Immune Support

Active Ingredients: Echinacea Fresh, Ivy Extract, Camu Camu, Ginger, Turmeric, Zinc

Inactive Ingredients: Natural Flavor, Guar Gum, Monk Fruit Sweetener, Citric Acid

Supplemen Serving Size 1 Sachet (5.4g) Servings per Container 3	t Fa	cts
	Amount Per Serving	% Daily Value
Calories	5	
Total Carbohydrate	1 g	<1%
Total Sugars	<1 g	†
Vitamin C (as Camu-camu (Fruit) Powder & Ascorbic Acid)	500 mg	833%
Zinc (as Zinc Gluconate)	15 mg	100%
Organic Turmeric Powder (Rhizome)	500 mg	†
Echinacea purpurea Extract (Aerial)	400 mg	†
Organic Ginger Powder (Root)	250 mg	†
English Ivy Extract (Leaf)	25 mg	t
*Percent Daily Values are based on a 2,000	calorie diet.	
† Daily Value Not Established		

OTHER INGREDIENTS: Natural Flavor, Guar Gum, Monk Fruit Extract, Citric Acid

The ingredients in the Immune Support Product have been included because of previously demonstrated benefits in supporting the immune system and reducing duration and symptoms of colds. The justifications for their inclusion are briefly described here:

Echinacea has shown to be clinically effective for supporting the immune system. Through preclinical and clinical studies, Echinacea has been shown to have multiple supportive effects on the immune system, such as stimulating macrophages and other cells of the innate immune system. Several clinical studies have also shown that Echinacea supports healthy immune function while reducing duration of colds. In one clinical study, Echinacea improved immune function in healthy people experiencing fatigue. The improvement in immune function in this study correlated with a higher measure of wellness. [4, 11, 12, 16, 17, 25, 27, 37]

Ivy Extract is a traditional European herb that has been used for centuries for supporting the respiratory system. Numerous preclinical and clinical studies have been conducted on Ivy Leaf Extract, which have substantiated its safe use for soothing cough, thought due to its expectorant and antispasmodic activity. In a review of 18 clinical trials, Ivy Extract was shown to be well established in supporting respiratory health. [3, 13, 32]

Camu Camu The Vitamin C in Immune Support is from a whole food source, called Camu Camu, a fruit from the Amazon with one of the highest Vitamin C contents in the world. Vitamin C is an important supportive nutrient in this formula for supporting the immune system. Additionally, Vitamin C acts as a cofactor for a number of enzymes and metabolic reactions in the body responsible for maintaining health and wellness. The Vitamin C from Camu Camu is also combined with naturally occurring bioflavonoids from its whole food source, providing a more full-spectrum

antioxidant support. In two controlled trials, showed that regularly administered vitamin C shortened the duration of colds, indicating a biological effect. They found a statistically significant dose-response, for the duration of common cold symptoms. [2, 8, 14, 19, 30, 41]

Ginger is a spice with a long history of traditional use for symptoms of a cold, including digestive discomfort, cough, and aches and pains. Clinical research shows that Ginger supports health through its benefits to the immune and respiratory systems, as well as promoting normal cytokine balance. [21, 24, 28, 29, 33]

Turmeric is a spice with a long history of traditional use for symptoms of a cold. Clinical and preclinical studies have shown it to support the immune & respiratory systems and support normal cytokine balance. Turmeric is used traditionally for wide uses, and as the research builds it shows that it is indeed capable of supporting multiple body systems, substantiating the tonic effect of this herb in maintaining overall health and vitality. [1, 15, 36]

Zinc is an essential mineral important for numerous physiological processes, notably, healthy immune response. Zinc has also been found to support immune health through a number of preclinical and clinical studies. In one study involving 100 people, zinc supplementation resulted in significant immune support. In another trial, supplementation with a zinc lozenge showed a significant decrease in the duration of cold symptoms. [6, 7, 9, 19, 20, 22, 34, 35]

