2.2. Scientific Rationale

The test product formulation is based on the most promising clinical research on natural ingredients to safely impact the immune system and reduce duration of the common cold. While the evidence to support the use of these individual active ingredients is growing, well-designed human clinical trials showing benefit are necessary to demonstrate efficacy of the test product's unique formulation.

The present study will include at least 200 adult participants in the general population who are seeking herbal remedies to reduce the duration of their common cold symptoms.

2.2.1.Potential Risk

Minimal risk is foreseen for participants through their participation in the study. All the ingredients composing the test product are Generally Recognized as Safe (GRAS) by the FDA for daily consumption at their present concentrations.

The ingredients in the test product have shown to have some theoretical drug interactions which have been listed in the appendix.

Potential side-effects have been observed in high doses which are significantly greater than the dose of the capsule as recommended in the instruction for use:

- · epigastric pain
- nausea
- vomiting
- loss of appetite
- abdominal cramps
- diarrhea
- headaches

This study is determined by Sponsor and Principal Investigator to be a Minimal Risk Study.

Minimal risk is defined by 45 U.S. Code of Federal Regulations (CFR) 46.102 (i) as follows:

"Minimal risk means that the probability and magnitude of harm or discomfort anticipated in the research are not greater in and of themselves than those ordinarily encountered in daily life or during the performance of routine physical or psychological examinations or tests."

Refer to: http://www.hhs.gov/ohrp/humansubjects/guidance/45cfr46.htm#46.102

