2.2.3. Minimization of Risks

Research participants will be carefully screened to meet enrollment criteria. Participants meeting exclusion criteria will not be enrolled. The study participant informed consent will be presented with clear description of the study requirements and opportunity to have questions answered before enrollment will be provided. Once an event occurs, review of symptoms will be

ascertained daily until symptoms have resolved or for 18 days. Reporting of adverse events will be reviewed routinely and in accordance with regulatory guidelines (21CFR, GCP) by the Principal Investigator. Participants with occurrence of worsening symptoms or adverse events will be advised to stop the product and may seek medical attention and exit the study.

3. Study Objectives

The purpose of the present study is to evaluate 1) the impact of the Immune Support test product on the duration of symptoms of the common cold in adult participants and 2) the subjective experience of these participants related to general health, common cold symptoms, and personal experience with the product. [13, 18, 29, 32]

This will be evaluated based on the primary and secondary endpoints. These endpoints, the analysis populations, and their respective measures are described below. Further details on the methods for measuring the outcomes can be found in the Study Outcome Measures and Analysis Plan sections.

Primary Endpoint:

The primary endpoint will be time to freedom from cold symptoms, with the clock starting at the onset of the cold. Where the onset is defined as the point in time when the participant experiences 2 or more cold symptoms. The primary analysis will be a Kaplan-Meier analysis of time to absence of all symptoms, based on the participants' self-report. There is no control group for the primary analysis. [5]

Secondary Endpoint:

- Secondary endpoints involve the duration and severity of the separate cold symptoms.
- Comparison against the participant's normal behavior.
- Net Promoter Score.
- Adverse events will be summarized.
- An additional data presentation will consist of results from both Treatment and Control in similar studies appearing in the literature. There will be no formal statistical comparison of results from this study and historical studies.

4.Study Design

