5.1. Selection of the study Population

The study population will consist of at least 200 participants who have completed the self-enrollment form and who meet the inclusion-exclusion criterion. The participants will otherwise be in good health.

The target sample size for this study is initially 200 participants, with a desired sample of 80 treated participants This sample size has been calculated to provide a reasonable estimate of the time to cold resolution, as further described in detail in the Statistical Considerations section.

At such time as 180 participants have been enrolled, the available data will be analyzed using a constant hazard model to determine if it seems realistic that the desired number of 80 treated participants will be met by the end of follow-up. If the expected number of treated participants is less than 80, the target sample size will be increased as needed, considering both the desire for 80 treated participants and the timelines of the trial sponsor. The actual outcomes of treated participants will not be considered in this analysis, merely whether or not enrolled participants have reported starting using the test product.

Enrollment will be stopped once the target number of participants have been enrolled; no further participants will be offered a place in the trial once the target sample size criteria has been met. All participants who have already been offered places, but who have not yet consented, will be allowed to participate as long as they have signed the study consent within 15 days and the total number of participants does not exceed 125% of the target (either 200 or the recomputed target if recomputation has been performed).

In order to ensure an age and sex distribution that is reasonably representative of the US population, enrollment may be stopped early in some age and sex groups.

Target population for this study are candidates who are in the general population who are seeking herbal remedies to reduce the duration of their common cold symptoms.

Participants will be enrolled from across the United States. No participants will be enrolled outside of the United States. It is expected that the geographical distribution of the participants enrolled in the study will correlate with the geographical distribution of the general population across the United States.

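### The primary hypothesis and stated purpose ask whether the product shortens colds, which one uncontrolled Kaplan-Meier curve cannot answer; restate the aim as estimation

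*Combined protocol and SAP*

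**What the plan says.** Four places frame the aim as a question of effect, with different strength.

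- Section 2.1 is flatly directional. The primary hypothesis, stated for the present study, is that "the Immune Support test product will reduce the time to freedom from cold symptoms".
- The synopsis objective poses it as a question to be settled: "The purpose of this study is to demonstrate whether or not this test product will" reduce duration.
- The title announces an evaluation of impact "in Reducing the Length of Cold Symptoms in Adults Suffering from the Common Cold".
- Section 3 sets out to evaluate "the impact of the Immune Support test product on the duration of symptoms of the common cold in adult participants".

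Other places describe a more modest study. The synopsis continues: "These data will be used to describe the performance currently, and potentially to design a two-arm trial in the future". Section 5.1 justifies the numbers as estimation: "This sample size has been calculated to provide a reasonable estimate of the time to cold resolution".

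The design matches the modest version. Section 4 specifies a single arm. The synopsis and Sections 3, 4.4 and 7.1 say that the primary analysis, a Kaplan-Meier analysis of self-reported symptom freedom, has no control group. Those places and 7.3 rule out formal comparison with historical studies. Section 7.3 limits formal comparisons to covariate analyses. Section 7.2 nevertheless expects the sample to allow a reasonable comparison with the cited zinc lozenge trial. Section 11 lists the absent concurrent control as a limitation.

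**The concern.** To say that the product reduces duration is to compare the duration seen with the duration that the same people would have had without it. The study does not measure the second quantity and the plan does not assume a value for it. Colds resolve without treatment, so a short median is compatible with a useful product and with an inert one.

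The stake is what the trial may conclude. Section 10 intends publication. A report written against the hypothesis in 2.1 would have to say whether it was supported, and nothing in the analysis provides a basis for either answer. Section 11 admits the missing control but does not draw the consequence, namely that the primary hypothesis goes untested here.

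**Working it through.** **1. The plan's own figure.** Section 7.2: 200 enrolled × 0.40 expected to have a cold = 80. This reproduces. It is a head count only. The documents give no alpha, power, effect size, reference duration or margin, so there is no hypothesis-test sample size to reproduce.

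**2. What a test of reduction needs, against what the plan supplies.**

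| Needed | In the plan |
|---|---|
| Concurrent comparator | None (Sections 4, 7.1) |
| Or a fixed reference duration | None given |
| Or a formal historical contrast | Ruled out (7.1, 7.3) |
| A rule linking result to conclusion | None given |
| A formal test on the primary endpoint against any of these | None; formal comparisons are in covariate analyses only (7.3) |

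None of these needs is met.

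**3. Would a benchmark or more participants rescue it?** An illustration with assumptions that are not in the documents: exponential durations, a benchmark median B = 7 days, a product with no effect, a two-sided 5% test, d events, and a true untreated median U in this population.

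P(declare shorter) = Φ(√d · ln(B/U) − 1.96)

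With d = 80:

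- U = 7: Φ(0 − 1.96) = 2.5%
- U = 6.5: Φ(0.663 − 1.96) = 9.7%
- U = 6: Φ(1.379 − 1.96) = 28%
- U = 5: Φ(3.009 − 1.96) = 85%

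With ten times the events (d = 800) and U = 6: √800 × ln(7/6) = 4.36, and Φ(4.36 − 1.96) is about 99%. A larger sample makes a false claim more likely, because the error comes from an untreated duration that the design never observes.

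**4. What 80 treated participants can deliver as an estimate.** Assumptions: true median m = 7 days, Weibull shape k from 2 to 1.

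- Density at the median: f = k · ln2 / (2m), which is 0.0990 for k = 2 and 0.0495 for k = 1.
- Large-sample half-width: 1.96 · √(0.25/80) / f, which is 1.11 days for k = 2 and 2.21 days for k = 1. The full widths are therefore about 2.2 and 4.4 days with no loss.
- Simulation (1,500 runs per setting, times rounded up to whole diary days, censoring at day 18, log-transformed Kaplan-Meier interval), mean full width for k = 2 to 1: about 2.2 to 4.5 days with no early loss, 2.5 to 5.1 with 20% lost early, and 2.9 to 6.1 with 40% lost early. The last range depends somewhat on how the loss is modelled; another set-up gives 2.8 to 5.8.
- The interval is not symmetric. With k = 1 and no loss, the mean limits lie about 1.6 days below and 2.8 days above the estimate. A plus-or-minus figure would understate the upper limit.

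Early loss is a realistic input. Section 4.2 exits participants who take other cold remedies or receive a new prescription, 7.3 censors those who withdraw or stop reporting, and 7.2 itself mentions uncertain compliance.

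**The case against.** The strongest reply is that the protocol hides nothing. It says in four places that there is no control group and in five that there is no formal historical comparison. It calls the study a description that may feed a two-arm trial, and it lists the limitation. No success rule exists by which a reduction could be declared. All of this stands, and it keeps the matter to one of wording. It does not withdraw the hypothesis in 2.1, which is stated for this study.

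A reader might infer that the title, synopsis and Section 3 also assert a reduction. They do not. The title speaks of evaluating impact, the synopsis says whether or not, and Section 3 says evaluate. They pose the causal question without answering it, though the design cannot answer it either way. A reader might also take the remark in 2.2 that "well-designed human clinical trials showing benefit are necessary to demonstrate efficacy of the test product's unique formulation" as a claim that this study is such a trial. The text places the two side by side but does not say so.

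Two comparators might be offered. The literature display is explicitly informal. This study also enrols adults seeking herbal remedies, reached by advertisements aimed at people prone to colds, so likeness to published arms cannot be presumed. The secondary endpoint "Comparison against the participant's normal behavior" is not the primary contrast and has no analysis in 7.3; its lack of definition is a separate matter.

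Finally, precision figures do not measure this fault. That is right. They show only what the restated aim would yield.

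**Conclusion.** The point holds as a mismatch between aim and analysis: the primary hypothesis and stated purpose call for a contrast that the plan does not contain, so no outcome can confirm or refute them. This follows from the documents alone and needs no numerical assumption.

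Two stronger readings are not supported. The Kaplan-Meier analysis is not faulty; it is a sound way to estimate time to symptom freedom with censoring at day 18. Nor does the plan conceal the lack of a control or intend to declare success. The risk is over-interpretation when results are reported.

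As an estimate, the study is useful but not sharp: a mean full 95% interval for the median of about 2.2 to 4.5 days with no early loss, and about 2.9 to 6.1 days with 40% loss. These figures rest on 80 treated participants and on an assumed median of 7 days and Weibull shape of 2 to 1. The change should be made; it is not a reason to hold the study.

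**What to change.** 1. In Section 2.1, the synopsis and Section 3, replace the reduction wording with: *to estimate the distribution of time from cold onset to symptom freedom (Kaplan-Meier median with 95% confidence interval, follow-up censored at 18 days) in adults taking the test product, and to inform a possible two-arm trial; no conclusion about reduced duration will be drawn from this single-arm estimate or from the literature display.*
2. Keep the directional statement only as a hypothesis for a later controlled trial.
3. In 7.2, call the comparison with the cited zinc lozenge trial descriptive. If a precision figure is added, give asymmetric limits, label median, shape and loss as assumptions, and include early loss, for example with the ranges above.
4. Align the title if it is being amended anyway.

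The cost is a wording amendment, to be kept consistent with the IRB review in Section 8 and, if the title changes, the registration in Section 10. The targets of 200 enrolled and 80 treated and the primary analysis do not change. The downside for the sponsor is a more modest claim.
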